### **13.8. Safety Analyses**

All subjects will be evaluable for safety. Adverse events that occur after a subject is entered (signs informed consent), but before the patient receives study drug, will not be recorded on the CRF unless the investigator believes that the events may have been caused by a protocol procedure. Safety analyses will include summaries of the incidence of adverse events by maximum CTCAE

grade (version 4.03; NCI 2010) that occur during the study treatment period or within 30 days of the last dose of study treatment or until alternate therapy is started, regardless of causality or relatedness to study drug. The safety-related outcomes that will be summarized include:

- Adverse events,
- TEAEs,
- SAEs,
- Deaths,
- Discontinuations due to adverse events,
- Extent of exposure to study drug treatment,
- Hospitalizations,
- Use of key concomitant medications.

Analyses for data with discrete dates (for example, death date and start/stop dates of concomitant medications) will be performed through 30 days after the patient has been discontinued from study treatment or until alternate therapy is started. Adverse events will also be analyzed in this time frame. After 30-day post-discontinuation follow-up, only those SAEs that are thought to be related to study treatment or protocol procedure should be reported immediately to AROG or its designee. For these events, the patient must be followed until the event has resolved or stabilized.

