#### 14.1.2. Serious AE (SAE)

An adverse event that results in any of the following outcomes:

- Death
- Life-threatening adverse event (real risk of dying)
- Hospital admission
- Prolongation of hospitalization
- Persistent or significant disability/incapacity/or change in psychosocial status
- Congenital anomaly
- Requirement of intervention to prevent permanent impairment or damage

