#### **14.4. Adverse Event Reporting**

AROG has standards for reporting AEs that are to be followed regardless of applicable regulatory requirements that may be less stringent. Lack of drug effect is not an AE in clinical trials, because the purpose of the clinical trial is to establish drug effect.

Adverse Events (AEs) will be evaluated according to CTCAE version 4.03 and documented in medical record. After the Informed Consent Document (ICD) is signed, study site personnel will record the occurrence and nature of each patient's pre-existing conditions, including clinically significant signs and symptoms of the disease. During the study, site personnel will record any change in the pre-existing condition(s) and the occurrence and nature of any new adverse events.

All AEs related to protocol procedures are reported to AROG or designee. All AEs occurring after the patient receives the first dose of study drug must be reported to AROG or its designee via CRF. Investigators will be instructed to report to AROG or its designee their assessment of the potential relatedness of each AE to protocol procedure, studied disease state, study drug, and/or drug delivery system via CRF.

For all AEs, the investigator should specify:

1. ***Seriousness:*** Seriousness of an AE is defined by the criteria described in Section 10.1. A severe AE should not always be considered as serious.
2. ***Date of onset and its duration (start and end dates):*** The investigator should follow up the outcome of any AEs until they return to normal or consolidation of the subject's condition. All adverse events still evolving at the end of the study are to be followed up by the investigator until their resolution or stabilization.
3. ***Severity:*** (using NCI CTCAE v.4.03),

4. **Action taken with respect to study drug:** (no action taken; study drug dosage adjusted/temporarily interrupted; study drug permanently discontinued due to this adverse event; hospitalization/prolonged hospitalization), corrective treatment/therapy given, additional investigations performed
5. **Outcome:** Resolved/Recovered, recovering/resolving, not recovered/resolved, recovered/resolved with sequelae, unknown
6. **Relatedness:** If an AE is related or not related to study drug

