The following events **are not** to be considered as a SAE:

- Any event requiring short consultation in a hospital
- An external treatment in a hospital emergency service
- Any event clearly related to disease progression
  - Disease progression can be considered as a worsening of a patient's condition attributable to the disease for which the investigational product is being studied. It may be an increase in the severity of the disease under study and/or increases in the symptoms of the disease. The development of new, or progression of existing metastasis to the primary cancer under study should be considered as disease progression and not an AE or SAE. Events that are unequivocally due to disease progression should not be reported as AEs or SAEs during the study.
- Hospitalization (1 night or more) or hospitalization prolongation for one of the following reasons:
  - Planned hospitalization for routine intervention
  - Hospitalization or intervention requested by the protocol
  - Hospitalization for explorations not related to a modification of the subject's health
  - Hospitalization for comfort or for social reasons (for example: hospitalization of an elderly person due to dependence on his partner who was hospitalized)
  - Hospitalization not related to a subject's health worsening and not related to the study objectives (for example: plastic surgery)

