#### **14.8. Deaths**

All deaths that occur during the study should be reported as follows:

- Death, which is unequivocally due to disease progression, should be communicated to the study monitor at the next monitoring visit and should be documented in the CRF module, but should not be reported as a SAE during the study
- Where death is not clearly due to disease progression of the disease under study the AE causing the death should be reported to the study monitor as an SAE within 24 hours of becoming aware of the event. The report should contain a comment regarding the co-

involvement of progression of disease, if appropriate, and should assign a single primary cause of death together with any contributory causes

- Deaths with an unknown cause should always be reported as a SAE (within 24 hours of becoming aware of the event) but every effort should be made to establish a cause of death. A post-mortem may be helpful in the assessment of the cause of death, and if performed, a copy of the post-mortem results (with translation of important parts into English) should be reported in an expedited fashion to the sponsor within the usual timeframes

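### Section 14.5 removes emergency-service and short-consultation events from the SAE class without saving the other seriousness criteria in Section 14.1.2

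*Combined protocol and SAP*

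**What the plan says.** Section 14.1.2 defines a serious adverse event as "An adverse event that results in any of the following outcomes" and lists seven outcomes. Two of them are "Life-threatening adverse event (real risk of dying)" and "Requirement of intervention to prevent permanent impairment or damage". Hospital admission is a separate item in the same list.

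Section 14.5 ends with a list of events that are not to be treated as SAEs. Its opening entries are "Any event requiring short consultation in a hospital" and "An external treatment in a hospital emergency service". The remaining entries are events clearly due to disease progression and hospital stays for certain named reasons.

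Section 14.4 tells the investigator how to judge seriousness: "Seriousness of an AE is defined by the criteria described in Section 10.1". Section 10.1 is the screening assessment list and contains no seriousness criteria.

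Section 13.8 counts SAEs among the planned safety summaries, under "The safety-related outcomes that will be summarized include". Safety and tolerability is one of the primary objectives in Section 6.1.

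**The concern.** The two lists sort events by different rules. Section 14.1.2 goes by outcome. The two opening exclusions in 14.5 go by setting, and the second list is worded as an outright exclusion. An event with a real risk of death that is treated in an emergency service and followed by discharge satisfies both lists, and the protocol does not say which prevails.

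Several things depend on SAE status:

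- **Notification.** Section 14.5 requires the sponsor to be told of an SAE within 24 hours. For other adverse events, the induction and consolidation keys in Appendix IV ask only for reporting at least monthly. After Day 1, maintenance assessments may be two months apart, with a one-month tolerance.
- **Onward reporting.** The SUSAR and IRB duties in Section 14.5 apply to serious events.
- **Late capture.** In long-term follow-up, Section 14.6 asks only for SAEs thought related to treatment or procedures to be documented on the CRF.
- **Analysis.** The SAE summary in Section 13.8 counts only what was classed as serious.

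**Working it through.** No arithmetic applies. The check sets the sections side by side.

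**Step 1. Does setting matter in 14.1.2?** Only for the two hospital items (admission and prolonged stay). The other five outcomes are serious wherever care is given, and any one is sufficient.

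**Step 2. Do the 14.5 entries carry a condition?** The disease-progression entry is limited by cause, and the hospital-stay entry by a closed list of reasons. The consultation entry covers any event of that kind, and the emergency-service entry covers any external treatment there. Neither requires that other seriousness criteria be absent.

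**Step 3. Is each setting-free outcome protected elsewhere?**

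| Outcome in 14.1.2 | Separate text that keeps it reportable |
|---|---|
| Death | Yes, 14.8, unless unequivocally due to progression: "the AE causing the death should be reported to the study monitor as an SAE within 24 hours" |
| Congenital anomaly | Yes, 14.9.1 |
| Life-threatening | None found |
| Disability or incapacity | None found |
| Intervention to avert lasting harm | None found |

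Section 14.7 adds that new cancers will generally be serious, but that does not reach the three unprotected rows.

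**Step 4. Does a cross-reference settle it?** No. The pointer in 14.4 leads to Screening instead of 14.1.2. The same item in 14.4 warns that a severe event is not always serious, so a grade 4 rating does not by itself restore SAE status.

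**Step 5. Apply both lists to example events.**

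| Event (hypothetical) | 14.1.2 | 14.5, literal |
|---|---|---|
| Life-threatening arrhythmia treated in an emergency service, patient sent home | SAE | Not an SAE |
| Outpatient drainage to avert permanent damage, done at a short hospital consultation | SAE | Not an SAE |
| Either event with an unplanned admission because of it | SAE | SAE |

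The first two rows conflict, and admission alone removes the conflict.

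**Step 6. What survives misclassification?** Under 14.4, adverse events after the first dose go on the CRF with severity and relatedness. Section 13.8 tabulates them by maximum CTCAE grade. The stopping rules in 13.2.1 to 13.2.3 count deaths and crenolanib-related non-hematologic grade 4 events, so SAE status does not enter them.

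**The case against.** The best defence is that 14.1.2 is the definition and the 14.5 list merely clarifies what counts as hospital admission. Apart from disease progression, every entry there concerns hospital contact or a hospital stay. Section 14.5 also asks the investigator to assess seriousness, and 14.4 speaks of seriousness criteria even though its section number is wrong. A careful site could read it this way. That reading is reasonable, so the finding is that such an event *can* be classed as non-serious, not that it will be. The protocol does not state that reading, however, and the exclusion is written without a condition.

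It is also fair that on-treatment events stay visible by grade and that the stopping rules are untouched. This narrows the consequence to notification, expedited routing, the SAE table and late follow-up.

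A reader might infer more in three ways that the documents do not support.

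- *That SAE counts in maintenance are biased low compared with induction and consolidation.* Section 10.3 assumes a hospital stay for chemotherapy only. Section 8.1 expects patients to be discharged while on crenolanib during induction and the first consolidation cycle. SAE collection starts only after a first tablet, which follows the end of cytarabine. Outpatient exposure is therefore not confined to maintenance, and 13.8 plans no comparison between periods.
- *That the undercount can be given a percentage.* No rate of serious events treated without admission appears anywhere, so an assumed share would simply return itself as the answer.
- *That all emergency-service treatment is excluded.* The entry says external treatment, which appears to mean outpatient care.

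One might also ask why the disease-progression entry is not challenged. It is defined by cause, is explained at length in 14.5 and agrees with 14.8, so it is a deliberate exclusion and not a by-product of where care was given.

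**Conclusion.** The contradiction between 14.1.2 and 14.5 stands and should be corrected. On a literal reading of 14.5, an outpatient event that is life-threatening, disabling or in need of intervention to avert lasting harm can lose SAE status because it was handled at a short hospital consultation or in an emergency service.

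During treatment the loss is the 24-hour report, the SUSAR and IRB route and a place in the SAE summary. In long-term follow-up the event might not be documented at all. That is stated as a possibility because 14.4 asks for all adverse events after the first dose with no end date, and 14.6 also requires persisting drug-related toxicity to be followed.

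The direction of any error is downward for SAEs. Its size cannot be derived: it is zero if every site reads the list as limited to admission, and otherwise depends on how many qualifying events are managed only in these settings. The conclusion rests on the wording alone and assumes no event rate.

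**What to change.** In Section 14.5, state that the consultation, emergency-service and hospitalization entries do not by themselves meet the hospitalization criterion, and that an event meeting any other criterion in 14.1.2 remains an SAE. Leave the disease-progression entry as it is. In Section 14.4, change the seriousness cross-reference from Section 10.1 to Section 14.1.2. Carry the same sentence into any SAE completion guidance given to sites.

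The cost is a short protocol edit and a few more SAE reports. No dose, schedule, stopping rule or planned analysis changes.

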#### **14.6. Follow-up of Adverse Events**

All adverse events will be followed up according to Good Clinical Practice.

**During Treatment:** During study, site personnel will track any change in the condition(s) and the occurrence and nature of any AEs and record the highest grade of the adverse event per cycle on the CRF. CTCAE grading will be assigned before each visit for any adverse events experienced during the previous visit period.

**Preparation for transplant:** Once patient enters conditioning prior to transplant, crenolanib will be held (72 hours prior to start of conditioning). Patients will not be followed for safety once conditioning starts. If patient receives maintenance crenolanib following transplant, safety will be assessed once patient restarts crenolanib (per protocol).

#### **Discontinuation due to relapse:**

Patients who have discontinued therapy due to relapse will be followed for safety for 30 days post last dose of crenolanib or until start of another therapy or death, whichever comes first.

#### **Discontinuation due to toxicity:**

Patients who have discontinued therapy due to toxicities attributable to study drug will be followed for safety for 30 days post last dose of crenolanib or until start of another therapy or death, whichever comes first.

**Long-Term Follow-Up Period:** Only new and ongoing serious adverse events (SAEs) thought to be related to study treatment or protocol procedures should be documented on the CRF and immediately reported to AROG or its designee via the designated transmission method. If drug-related toxicity is present beyond 30 days post-discontinuation, patients must be followed at least for 30 days or until the toxicity resolves.

#### **14.7. Miscellaneous adverse events**

**New safety issues:** Any new safety data that could lead to re-evaluate the ratio between the benefits and the risks of the research, or that could be sufficiently important to consider modifications of the research documents, the research management or, if need be, the drug utilization.

**New cancers:** The development of a new cancer should be regarded as an AE and will generally meet at least one of the serious criteria. New cancers are those that are not the primary reason for the administration of the study treatment and have been identified after the subject's inclusion in this study. They do not include metastases of the original cancer.

#### **14.8. Deaths**

All deaths that occur during the study should be reported as follows:

- Death, which is unequivocally due to disease progression, should be communicated to the study monitor at the next monitoring visit and should be documented in the CRF module, but should not be reported as a SAE during the study
- Where death is not clearly due to disease progression of the disease under study the AE causing the death should be reported to the study monitor as an SAE within 24 hours of becoming aware of the event. The report should contain a comment regarding the co-

involvement of progression of disease, if appropriate, and should assign a single primary cause of death together with any contributory causes

- Deaths with an unknown cause should always be reported as a SAE (within 24 hours of becoming aware of the event) but every effort should be made to establish a cause of death. A post-mortem may be helpful in the assessment of the cause of death, and if performed, a copy of the post-mortem results (with translation of important parts into English) should be reported in an expedited fashion to the sponsor within the usual timeframes

#### **14.9. Pregnancy**

Nothing is known about the effects of crenolanib on reproductive function. Women of reproductive potential and fertile men will be informed as to the potential risk of procreation while participating in this trial.

If the investigator has been informed that a female subject is pregnant during the study period:

1. The investigational product should be immediately discontinued and the planned safety assessments should be performed
2. The investigator must immediately notify the study monitor, complete the Pregnancy Report Form, and send it to Arog Pharmaceuticals by e-mail: [[contact]](mailto:[contact]) or [contact].
3. Follow-up of the pregnancy will be mandatory until the outcome has been determined.

*Nota bene:* In order to follow the pregnancy of the wife of a subject included in the study, consent or agreement of the subject's wife should appear in the medical file of the subject.

##### **14.9.1. Maternal exposure**

Pregnancy itself is not regarded as an adverse event. Congenital abnormalities/birth defects and spontaneous miscarriages should be reported and handled as SAEs. Elective abortions without complications should not be handled as AEs. The outcome of a pregnancy should be followed up and documented even if the patient was withdrawn from the study.

If a pregnancy occurs during exposure to investigational product or in the 30 days after discontinuing investigational product, then investigators or other site personnel must inform the sponsor immediately, or **no later than 24 hours** of when he or she becomes aware of it. The same timelines apply when outcome information is available.

##### **14.9.2. Paternal exposure**

Pregnancy of a patient's partner is not considered to be an adverse event. However, any conception occurring from the date of dosing until 16 weeks after dosing should be reported to the sponsor and followed up for its outcome.

#### **14.10. Overdose**

To date there have been no instances of patients who were inadvertently overdosed. Clinical studies have shown an apparent crenolanib half-life of approximately 8 hours. It is anticipated that

crenolanib would be metabolized and excreted within 5 half-lives of the drug. No specific antidote exists for the treatment of crenolanib overdose. Investigators will be advised that any patient who receives a higher dose than that intended should be monitored closely, managed with appropriate supportive care and followed up expectantly.

If an overdose occurs in the course of the study, then investigators or other site personnel must inform the sponsor immediately, or **no later than 24 hours** of when he/she becomes aware of it.

Such overdoses should be recorded as follows:

- An overdose with associated AEs/SAEs is recorded as the AE diagnosis/symptoms on the relevant AE/SAE modules in the eCRF.
- An overdose with no associated symptoms should be documented on the eCRF module for dosing of study drug.

## 15. DATA COLLECTION AND MANAGEMENT

To ensure accurate, complete, and reliable data, AROG or its representatives will do the following:

- Provide instructional material to the study site, as appropriate.
- Sponsor a start-up training session to instruct the investigators and study coordinators. This session will give instruction on the protocol, the completion of the CRFs, and study procedures.
- Conduct periodic teleconferences (approximately twice a month) with each study site to discuss current patients on trial, available pharmacodynamics/pharmacokinetic data, regulatory issues and other updates as applicable.
- Make periodic visits to the study site.
- Be available for consultation and stay in contact with the study site personnel by mail, telephone, and/or fax.
- Review and evaluate CRF data and use audits to detect errors in data collection.
- Conduct a quality review of the database.

In addition, AROG or its representatives will periodically check a sample of the patient data recorded against source documents at the study site. The study may be audited by AROG or its representatives, and/or regulatory agencies at any time. Investigators will be given notice before an audit occurs.

To ensure the safety of participants in the study, and to ensure accurate, complete, and reliable data, the investigator will keep records of laboratory tests, clinical notes, and patient medical records in the patient files as original source documents for the study. If requested, the investigator will provide the sponsor, applicable regulatory agencies, and applicable ethical review boards (ERBs) with direct access to original source documents.

### 15.1. Data Capture System

An electronic data capture system will be used in this trial. Case report form (CRF) data will be encoded and stored in a clinical trial database. Any data that will serve as the source document will be identified and documented in the site's study file.

### 15.2. Data Safety Monitoring Plan

AROG and Investigator, or his/her designee, will have periodic teleconferences (approximately twice a month) with each study site to discuss current patients on trial, available pharmacodynamics/pharmacokinetic data, regulatory issues and other updates as applicable.

AROG will have Data Safety Monitoring meetings at least every six months or for every 6 patients enrolled per cohort. At these meetings, compiled patient data including responses and safety analysis will be discussed.

